### Aim 2:

Statistical Analysis: Our primary analysis will compare rates of UACR testing and evidence-based T2D therapy by PCP cluster in the intervention and baseline time periods. Paired Student's t-test will be used to determine differences in testing and prescribing rates by study arm at 3 months post-intervention compared to 3 months pre-intervention among all PCPs who agree to participate in the intervention. At study completion, we will ask all study PCPs to complete a user experience survey to determine their perceived value of the study activities, suggestions for intervention improvement (with focus on facilitated integration into the clinical encounter), perceptions regarding the clinical benefit for their Hispanic/Latinx patients with T2D, and interest in further refining the intervention for use in a future hybrid effectiveness-implementation trial. Geocoded patient data are extracted from Duke's Clinical Research Data Mart (CRDM). CRDM supports data provenance and reproducibility by providing access to curated Duke patient data through reproducible SQL queries.

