The influx of patients with T2D to DOC and LCHC from our screening events will directly relate to Aim 2 of this proposal (Figure 1).

**Specific Aim 2:** Modify and pilot test a provider-facing intervention to promote guideline concordant testing and evidence-based therapy provision for Hispanic/Latinx and non-Hispanic Black individuals with T2D.

We will leverage available educational resources (e.g. ADA, NKF) to inform the development of an intervention to support PCP's at the clinical encounter that integrates thorough patient education with involvement by key clinical stakeholders (e.g. clinical and pharmacy champions) to optimize T2D care for Hispanics/Latinx at the clinical encounter.

**Study Population:** Approximately 50 PCPs at DOC (Durham, NC) who care for Hispanic/Latinx patients with CKD and/or CKD risk factors.

[figure not shown]
**Intervention Cohort:** PCPs caring for ~200 Hispanic/Latinx and non-Hispanic Black patients with T2D. These providers will receive study team feedback on optimal T2D screening and management.

**Study Setting:** The DOC will serve as our recruitment site for this aim. The DOC is a primary care clinic in Durham, NC that has a long and illustrious history as an ambulatory practice site for internal medicine (IM) physicians and their patients. DOC has 79 PCPs who see approximately 20,000 visits per year, including 5,000 unique patients. DOC's patient population consists primarily of racial and ethnic minorities.

**Study Design:** Pre and post comparison of the study intervention versus 3-month baseline data at the PCP level for Hispanic/Latinx patients with T2D.

**Study Intervention:** The study intervention is designed to support PCP's standard of care services and will not include any new activities or guidelines outside of standard of care practices that would require approval from the clinics. This support includes providing PCP's with available educational resources (ADA, NKF) for their patients, pharmacy champions and clinical champions to conduct thorough patient chart reviews in order to make recommendations for medications and tests as part of their standard of care services.

The study intervention consists of four steps (Figure 2): Chart Review, Tailored Recommendations, PCP Communication and Patient T2D Care.

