## Selection of Subjects

- List inclusion/exclusion criteria and how subjects will be identified.

Aim 1:

Inclusion Criteria: Age 18 or older at time of screening and self-identifying as Hispanic/Latinx ethnicity.

Exclusion Criteria: Inability to be reached by telephone.

Aim 2:

Study Population: PCPs at DOC (Durham, NC) who care for Hispanic/Latinx and non-Hispanic patients with T2D

Patient Inclusion Criteria:

- Age 18 or older at time of screening
- At least one PCP visit at DOC between January 1, 2021-June 30, 2023
- Self-identifying as Hispanic/Latino/Latino/Latinx or non-Hispanic Black
- Diagnosis of T2D at last PCP visit defined by a) ICD-10 code or b) HbA1C  $\geq 6.5$  or c) diabetes medication use

Patient Exclusion Criteria:

- Type 1 diabetes

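### Aim 2's single-cohort test of 3 months after against 3 months before estimates change over time and cannot separate the intervention from trend, season or case mix

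*Combined protocol and SAP*

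**What the plan says.** Design & Procedures, Specific Aim 2, sets the design as "Pre and post comparison of the study intervention versus 3-month baseline data at the PCP level". It describes one group, the intervention cohort: "PCPs caring for ~200 Hispanic/Latinx and non-Hispanic Black patients with T2D". The study population is "Approximately 50 PCPs at DOC (Durham, NC) who care for Hispanic/Latinx patients with CKD and/or CKD risk factors".

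Under Data Analysis & Statistical Considerations, Aim 2, the primary analysis is to "compare rates of UACR testing and evidence-based T2D therapy by PCP cluster in the intervention and baseline time periods". The test is a paired Student's t-test, among PCPs who agree to take part, of "differences in testing and prescribing rates by study arm at 3 months post-intervention compared to 3 months pre-intervention".

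The text mentions no randomization, concurrent comparison group, earlier baseline periods, trend or season adjustment, or matching of the two windows by calendar month. It gives no alpha, power, effect size or expected drift for Aim 2.

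**The concern.** Each PCP is untreated in the first window and treated in the second, so intervention and calendar time coincide exactly. Pairing removes stable differences between PCPs. It does not remove a change that all PCPs share.

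The protocol itself gives two reasons why rates might move without the intervention:

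- **Uptake of newer drugs.** One of the two prescribing queries in the chart review asks about SGLT2 inhibitors or GLP-1 receptor agonists, combined in one yes/no item. Background & Significance (item 2) calls these newer therapies.
- **Case mix.** Specific Aim 2 expects patients with T2D found at the Aim 1 screening events to come to the same clinic.

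Season is a third possibility, because two adjacent 3-month windows fall in different parts of the year.

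What is at stake is how the pilot is read. The result is meant to inform a larger effectiveness-implementation trial, and a significant change in this test could not be attributed to the intervention.

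**Working it through.** The plan states no figure for Aim 2 that could be reproduced. The check has three parts.

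**1. Size of the bias.** If the two windows are adjacent (an assumption), their midpoints are 3 months apart. A background slope of b points per month then adds 3 × b points to the estimate:

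- b = 0.5 adds 1.5 points.
- b = 1 adds 3 points.
- b = 2 adds 6 points. This slope equals 24 points a year, so it is a high value.

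These slopes are assumptions; the documents give none.

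**2. False-positive rate with no intervention effect.** Inputs from the documents are about 50 PCPs and about 200 patients, so 200 / 50 = 4 patients per PCP. Assumptions are that all 4 are seen in each period, a 30% base rate, a between-PCP SD of 0.4 on the logit scale, and a two-sided 5% level.

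Approximate SE of the mean change from p0 to p1 = sqrt{[p0(1−p0) + p1(1−p1)] / (50 × 4)}.

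| Drift | SE | Drift / SE | P(p<0.05), normal approximation | Simulated paired t-test |
|---|---|---|---|---|
| 1.5 points | sqrt[(0.2100+0.2158)/200] = 0.0461 | 0.33 | 6% | about 6% |
| 3 points | sqrt[(0.2100+0.2211)/200] = 0.0464 | 0.65 | 10% | about 10% |
| 6 points | sqrt[(0.2100+0.2304)/200] = 0.0469 | 1.28 | 25% | about 23% |

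The last row runs from 23% to 25%, depending on how the drift is applied to the individual PCPs' rates.

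A second simulation used a 21% base rate, which is the national UACR testing figure in Background & Significance and not a DOC baseline, with an assumed ICC of 0.05. With 4 patients per PCP per period, drifts of 3 and 5 points gave 11% and 22%. With 2 patients (the 200 split over both periods) they gave 9% and 14%.

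The lower rates with fewer patients reflect lower precision. The bias stays equal to the drift.

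**3. Precision of a trend-adjusted alternative.** With equal monthly counts, independent months and unit variance per month, the 3-v-3 contrast has variance 1/3 + 1/3 = 0.667. For a segmented model, the variance of the intervention step is the matching diagonal element of (X'X)^-1. The table gives that variance and, in brackets, the SE ratio sqrt(variance / 0.667), with 3 post-intervention months throughout.

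| Baseline months | Trend and step only | Plus one annual sine/cosine pair | Plus month indicators |
|---|---|---|---|
| 27 | 0.508 (0.87) | 0.629 (0.97) | 0.714 (1.04) |
| 24 | 0.533 (0.89) | 0.704 (1.03) | 0.875 (1.15) |
| 12 | 0.805 (1.10) | 2.115 (1.78) | not estimable |

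Once season is included, 24 to 27 baseline months give an SE between 3% smaller and 15% larger than the 3-v-3 contrast. With 12 months the SE is at least 78% larger.

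**The case against.** The strongest defence is that this is a pilot meant to establish feasibility, for which a pre/post design is legitimate. The plan sets no alpha and does not say that the change will be reported as causal. At a drift of 1.5 points the error rate is close to nominal. All of this stands and lowers the severity. It does not remove the problem, because the plan makes this comparison its primary analysis and does not limit its interpretation.

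A reader might also infer more than the documents support:

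- **That the study-arm wording points to a second arm or causes the confounding.** The preceding sentence defines the comparison as one between time periods. The phrase is a wording slip, and the confounding comes from the design.
- **That both prescribing outcomes concern newer drugs with rising use.** The other query is RAAS inhibitors, which Background & Significance calls longstanding. No rise at DOC is reported for any class.
- **That the bias must favour the intervention.** Newly identified, untreated patients from Aim 1 could lower prescribing rates in the second window. The inflow is also limited: about 150 people are screened, only some will have T2D, and DOC is one of several places they may go.
- **That a 27-month baseline is already in the plan.** The criterion "At least one PCP visit at DOC between January 1, 2021-June 30, 2023" defines patient eligibility. It is not stated to be the analysis extract, and no intervention dates are given.
- **That adjusting for trend gains precision.** This holds with 24 or 27 baseline months only if season is left out.
- **That the remaining PCPs are a ready control group.** The text says "DOC has 79 PCPs who see approximately 20,000 visits per year", and 79 − 50 = 29. Those 29 may have few eligible patients, may have declined, and work in the same clinic, so contamination is possible. Even if they were sound controls, a difference-in-differences would raise the SE from about 4.0 to 6.6 points (21% base rate, 4 patients per PCP per period).

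**Conclusion.** The concern holds in this form: the planned test estimates change over time in one cohort, and the intervention cannot be separated from trend, season or case-mix change. This follows from the design and needs no numerical assumption.

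The size of the resulting error is unknown. The rates of about 6%, 10% and 23% are illustrations that rest on the assumed drifts, the 30% base rate, 4 patients per PCP per period, and a change shared by all PCPs. They do not show that a false-positive result is likely at DOC.

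Because the study is a feasibility pilot, this should be fixed but does not invalidate it. The correction changes what the pilot may conclude and leaves its conduct as planned.

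**What to change.** In Data Analysis & Statistical Considerations, Aim 2:

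1. State that the paired 3-v-3 test estimates change over time and not intervention effect. Remove the reference to a study arm.
2. Before outcome data are examined, add a segmented regression on monthly EHR data for the same PCPs from the same CRDM source. Use as many pre-intervention months as can be extracted, preferably 24 or more. Include a trend, a season term, an intervention step and PCP clustering. Base any statement about intervention effect on this model.
3. Flag patients referred from Aim 1 and repeat the analysis without them.

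Any comparison with non-participating DOC PCPs should be labelled exploratory, for the reasons given above.

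The cost is a longer data extract, a link between Aim 1 participants and DOC records (which the protocol text does not describe), and some added wording. No new patients or procedures are needed. The segmented model assumes a shape for the trend, which can be checked by starting the series later. Its SE is about equal to the 3-v-3 contrast or up to 15% larger with 24 to 27 baseline months, and much larger with only 12. Those ratios assume independent months with equal counts. Independence is doubtful for prescribing status, which persists in the same patients, so the model should allow for correlation between months.

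If the sponsor does not want the second model, item 1 alone removes the risk of misreading, but the pilot then supports no statement about intervention effect.

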## Data & Safety Monitoring

- Summarize safety concerns, and describe the methods to monitor research subjects and their data to ensure their safety, including who will monitor the data, and the frequency of such monitoring. If a data monitoring committee will be used, describe its operation, including stopping rules and frequency of review, and if it is independent of the sponsor (per 45 CFR 46.111(a) (6)).

PCP's and PI will review patient data and test results to monitor the outcomes of their routine screening and intervention in Aim 1 and 2. The PI will be responsible for monitoring any safety concerns, including loss of confidentiality of study data. The PI will also be responsible for reporting any adverse events to the IRB.
